# **Nocturnal Hypertension and Sleep (Sleep BP Study)**

**NCT05062161**

**July 11, 2025**

## **1. Study Purpose and Rationale**

The purpose of this study is to examine the impact that sleep duration has on blood pressure levels during sleep. We will examine the effect of an 8-week sleep hygiene/extension intervention vs. control on sleep blood pressure.

### **Background:**

Blood pressure varies across the day, typically highest when awake and lower during sleep. Elevated nighttime blood pressure (nocturnal hypertension, defined as sleep blood pressure  $\geq 110/65$  mmHg) and reduced nighttime declines in blood pressure (“non-dipping”) are linked to higher risks of cardiovascular disease, target organ damage, and mortality. These patterns are present in 30–45% of the general population, but optimal strategies to address them remain unclear.

Short sleep duration, defined as fewer than 7 hours per night, affects more than one-third of U.S. adults and is associated with obesity, diabetes, hypertension, and increased mortality. Prior studies show that insufficient sleep is linked to higher nighttime blood pressure and non-dipping patterns. Experimental sleep restriction raises blood pressure, but there is limited evidence on whether extending sleep improves nighttime blood pressure. Small clinical studies suggest potential benefits, but these were conducted in specialized settings and relied on less widely validated measures. This study will build on that work by testing whether sleep extension in daily life can lower nighttime blood pressure.

## **2. Study Design**

Up to 66 participants will be enrolled following a two-step screening process: (1) completion of initial questionnaires, and (2) a two-week period of daily self-reported sleep assessments. Those meeting eligibility criteria will be consented and undergo a baseline visit. Baseline clinic blood pressure will be measured with a validated automated device after a 5-minute rest. All participants will complete questionnaires and be fitted with devices for sleep tracking, 24-hour ambulatory blood pressure monitoring, and 24-hour heart rate monitoring. Participants return the 24-hour devices and are then randomized 1:1 to either a sleep hygiene/extension education program or control education. Depending on group assignment, participants will attend a 60-minute educational session on either sleep hygiene/extension strategies or general sleep physiology. Over the 8-week study period, participants will receive weekly phone or video check-ins, complete questionnaires, and review progress and study materials. At the end of the study, participants will repeat the 24-hour blood pressure and heart rate monitoring before returning study devices.

## **3. Statistical Procedures**

Sample size calculations used a two-sided alpha of 5% and 80% statistical power. Enrolling 66 participants will provide a final sample size of 52, assuming 10% attrition and 10% with incomplete data. With this sample size, we will have 80% statistical power to detect a change in mean sleep systolic blood pressure and diastolic blood pressure between participants randomized to sleep hygiene/extension intervention vs. control. Mean sleep systolic and

diastolic blood pressure will be calculated at baseline and follow-up for participants randomized to sleep extension and sleep maintenance, separately. The change in mean sleep blood pressure from baseline to follow-up (the difference between baseline and follow-up sleep blood pressure) will be calculated and compared across randomization arms using a t-test.

**4. Recruitment:** Participants will be recruited through multiple approaches (e.g., flyers, community events).

Inclusion Criteria:

- English speaking adults
- Age 18 and older
- Sleep duration < 7 hours per night as assessed via daily self-report of sleep hours

Exclusion Criteria:

- Inability to read or write in English
- Pregnant or plans to get pregnant within study period
- Arm circumference >50 cm
- Lymphedema of the arm or unable to wear ABPM device for 24 hours or sleep monitoring device for 8 weeks
- End-stage renal disease (ESRD) on dialysis
- Unreliable internet or phone/text access
- High risk of Obstructive Sleep Apnea (OSA) (using the Berlin Questionnaire or diagnosis of OSA or use continuous positive airway pressure device)
- High risk of insomnia (using the Insomnia Severity Index), or a known prior history of insomnia, and/or use of prescription sleep aides
- High risk of depression (using the Patient Health Questionnaire Depression Scale: PHQ-8)
- Perimenopausal women who have hot flashes (using the Menopause Rating Scale (MRS) questionnaire, administered only to females age 45-65)
- Plan to travel out of state and/or internationally during the study period

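### Does the 80% power claim fail because the plan gives no blood pressure difference or SD to go with it?

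*Combined protocol and SAP*

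**What the plan says.** Section 3 (Statistical Procedures) reports the error rates, "Sample size calculations used a two-sided alpha of 5% and 80% statistical power", and the numbers, "Enrolling 66 participants will provide a final sample size of 52", the loss being explained as "assuming 10% attrition and 10% with incomplete data". It then draws the conclusion: "With this sample size, we will have 80% statistical power to detect a change in mean sleep systolic blood pressure", and likewise in diastolic pressure, in the comparison of intervention with control.

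Section 2 (Study Design) fixes the allocation: participants are "randomized 1:1 to either a sleep hygiene/extension education program or control education". Section 3 fixes the analysis: the change from baseline to follow-up in mean sleep blood pressure "will be calculated and compared across randomization arms using a t-test".

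No section gives a target difference in mmHg, a standardised effect, or an SD for the change in systolic or diastolic pressure. The only blood pressure value in the document is the 110/65 mmHg threshold in the Background, which defines nocturnal hypertension and is not a design effect.

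**The concern.** Power depends on four things: the true difference, the SD, the sample size and alpha. Section 3 gives the last two and omits the first two, so its 80% is tied to no stated effect and cannot be checked. One figure also covers two outcomes that need not share a difference or an SD.

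Interpretation is what would be at stake. A reader who takes the trial as adequately powered without qualification might treat a non-significant t-test as evidence that sleep extension does not lower sleep blood pressure. If the true effect were about half an SD, a non-significant result would be the more likely outcome even though the intervention worked.

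**Working it through.** **Inputs from the documents.** Two-sided alpha 5%, power 80%, 66 enrolled, 52 analysable, losses of 10% and 10%, and a t-test on change (all Section 3); 1:1 allocation (Section 2). The 26 per arm is derived: 52 / 2 = 26. The difference and the SD of change are not given.

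**Step 1: the plan's own figures.**
- Losses added: 66 × (1 − 0.20) = 52.8, against 52 stated.
- Losses compounded: 66 × 0.9 × 0.9 = 53.5.
- Working back from 26 per arm: 26 / 0.80 = 32.5, rounded up to 33, and 2 × 33 = 66.

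The enrolment figure reproduces. The 80% power cannot be reproduced, because two of its inputs are missing.

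**Step 2: the difference that gives 80% power at 26 per arm.** Write d for the true between-arm difference divided by the SD of the change score.
- Normal approximation: d = (1.960 + 0.842) × √(2/26) = 2.802 × 0.2774 = 0.777.
- t-test: noncentral t with 26 + 26 − 2 = 50 degrees of freedom and noncentrality d / √(2/26). Setting power to 80% gives d = 0.792.

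**Step 3: power at other true differences** (same noncentral t, two-sided, both rejection tails counted).

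| True difference (SD of change) | Power |
|---|---|
| 0.3 | 18.6% |
| 0.4 | 29.3% |
| 0.5 | 42.4% |
| 0.6 | 56.4% |
| 0.7 | 69.7% |
| 0.8 | 80.8% |

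Power reaches 50% at d of about 0.55. A miss is therefore the likelier outcome only for true differences below that.

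**Step 4: what 0.792 SD means in mmHg.** This needs an SD that the documents do not give. As an assumption, SDs of change of 6, 8, 10 and 12 mmHg give 0.792 × 6 = 4.8, 0.792 × 8 = 6.3, 0.792 × 10 = 7.9 and 0.792 × 12 = 9.5 mmHg. These values only illustrate the scale. Nothing in the documents favours one SD over another.

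**Step 5: what would differ if the inputs were written down.** The number enrolled, the allocation, the endpoint, the test and its alpha are all specified without them. Adding a difference and an SD to the sample size paragraph alters none of these, so the estimate and p-value would be the same.

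**The case for a change.** The strongest case for asking for a change is that the sample size paragraph is the trial's main quantitative justification and cannot be verified. Nothing at that point is marked as redacted. The Background says evidence on extending sleep is limited, so the result may be read closely whichever way it falls, and the plan names a t-test without committing to a confidence interval. The 95% interval would have a half-width of about 2.009 × √(2/26) = 0.56 of the observed SD, so a null result could leave moderate benefits open. Stating the two inputs would cost a sentence and no participants.

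Much of this stands. The omission is real, the 0.79 SD figure is correct, and a reader would be better served by seeing the planned difference and SD for each outcome, with their source.

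The step from there to a defect does not stand. Section 3 says a calculation was done; leaving out its effect size makes the 80% uncheckable, which is not the same as false. The plan does not claim 80% power against every possible change. Calling 0.79 SD large is a convention, and without an SD or an expected effect the documents cannot show it to be implausible. The plan nowhere says that a non-significant result will be read as no effect. A back-solved 0.79 SD written into the paragraph would only restate the sample size and would still not disclose what the sponsor planned for.

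**Conclusion.** No change to the plan follows. The power statement is incomplete: it omits the target between-arm difference and the SD of change for sleep systolic and diastolic pressure. It is not shown to be wrong, and 52 analysable participants are not shown to be too few.

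The design has 80% power at 0.79 SD of the change score for each outcome taken separately, and less than 50% below about 0.55 SD. This assumes 26 analysable participants in each arm, a two-sided 5% t-test on change, and a common SD in the two arms. Unequal losses would raise the detectable difference slightly. Any value in mmHg rests on an assumed SD.

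This is a gap in reporting. Analysts following Section 3 as written would compare the randomised arms by the same t-test and reach the same result whether or not the inputs were printed. Anyone reading a non-significant result should bear in mind that the trial could easily miss effects of around half an SD, but that is a caution for interpretation and calls for no revision of the design or analysis.

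### Sleep systolic and diastolic pressure are unranked outcomes for one question, with no primary outcome, testing order or success rule

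*Combined protocol and SAP*

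**What the plan says.** Section 1 states the aim as a single effect: "We will examine the effect of an 8-week sleep hygiene/extension intervention vs. control on sleep blood pressure". The Background gives it a direction, "testing whether sleep extension in daily life can lower nighttime blood pressure". Neither place chooses between systolic and diastolic pressure.

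Section 3 sets one error level, "Sample size calculations used a two-sided alpha of 5% and 80% statistical power", and makes one power statement for the two pressures together: "we will have 80% statistical power to detect a change in mean sleep systolic blood pressure and diastolic blood pressure between participants randomized". Mean sleep systolic pressure (SBP) and mean sleep diastolic pressure (DBP) are then obtained in each arm at both time points. Their changes "will be calculated and compared across randomization arms using a t-test".

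The document does not label either pressure primary or secondary, set an order of testing, divide or adjust alpha, or say whether a positive trial needs SBP, DBP, either or both. No redaction is visible at this point. That the two have equal standing is inferred from their parallel wording; nothing ranks one above the other.

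**The concern.** One question with two tests needs a rule that links the test results to the answer, and the plan has none. Two things follow.

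First, nothing prevents a claim about sleep blood pressure from resting on whichever pressure turns out significant. If that happens with each test at 5%, the false-positive rate for the claim is above its nominal level.

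Second, if the two tests disagree, the plan cannot say whether the trial's question was answered yes or no, even when both p-values are reported. For the same reason the 80% power figure has no single meaning: it could be the power for each outcome, for at least one, or for both, and these differ.

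**Working it through.** **Inputs from the documents.** Two-sided alpha 5% and power 80% (Section 3); 66 enrolled and 52 analysed, with 10% attrition and 10% incomplete data (Section 3); 1:1 allocation (Section 2), hence 26 per arm.

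**Assumed input.** The correlation ρ between the SBP and DBP test statistics is not given. I use 0.5 to 0.9 and show 0 as a limit.

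**1. The plan's own figures.** 66 × (1 − 0.20) = 52.8, or 52 rounded down; taking the losses in sequence, 66 × 0.9 × 0.9 = 53.5. The step from 66 to 52 reproduces to within two participants. The 80% power cannot be reproduced, because no detectable difference or SD is stated for either pressure. Solving backwards at 26 per arm, (1.96 + 0.84) × √(2/26) gives a standardised difference of 0.78 (0.79 with the t distribution). That is a separate gap and is not needed for this point.

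**2. Either outcome suffices, each tested at two-sided 5%, no effect on either.** With (Z₁, Z₂) bivariate normal with correlation ρ:

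- benefit direction: 1 − P(Z₁ < 1.96, Z₂ < 1.96), nominal 2.5%
- two-sided: 1 − P(|Z₁| < 1.96, |Z₂| < 1.96), nominal 5%

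**3. Both outcomes required, each with exactly 80% power.** Joint power = P(Z₁ < 0.84, Z₂ < 0.84). The chance that exactly one is significant is 2 × (0.80 − joint power).

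| ρ | False claim of benefit (either) | Two-sided error (either) | Joint power (both) | Exactly one significant |
|---|---|---|---|---|
| 0 | 4.9% | 9.75% | 64% | 32% |
| 0.5 | 4.5% | 9.1% | 69% | 23% |
| 0.7 | 4.2% | 8.4% | 71% | 17% |
| 0.9 | 3.5% | 7.0% | 75% | 10% |

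The independent case checks by hand: 1 − 0.95² = 9.75%, 1 − 0.975² = 4.9%, and 0.80² = 64%.

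A simulation of two-sample t-tests at 26 per arm (400,000 runs) agrees at ρ = 0.5, 0.7 and 0.9: benefit direction 4.6%, 4.2%, 3.6%; two-sided 9.1%, 8.4%, 7.1%.

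**4. Named primary tested first.** When neither outcome has an effect, a false claim requires the primary to be falsely significant. In the same simulation that rate was 5.0% two-sided and 2.5% in the benefit direction at every ρ.

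**5. Split alpha, 2.5% each.** For an outcome with exactly 80% power at 5%, the noncentral t at 26 per arm gives 71% power at 2.5%. If both outcomes have that effect, the chance of at least one significant result (normal approximation, critical value 2.24) is 85%, 82% and 77% at ρ = 0.5, 0.7 and 0.9.

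**The case against.** The strongest reply is that the harm depends on a rule the protocol does not contain. A reader might infer that the plan's error rate is 7% to 9%. The documents do not support that: they do not say that a win on either outcome counts, and pairing the two pressures in one sentence is equally open to a both-required reading, which inflates nothing. This stands. What the text shows is an undefined rule; the inflated rates are what one permitted reading would produce.

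A reader might also infer from the joint power figures that the trial is underpowered. That does not follow either. No both-required rule is stated, and the shortfall shrinks if either outcome has more than 80% power.

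It can also be said that the two-sided figures overstate the problem, because the Background is about lowering pressure. That is fair. The benefit-direction excess is 1 to 2 percentage points, and it should be read first.

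Next, sleep blood pressure could be read as two parameters, each with its own conclusion, since the Background defines nocturnal hypertension by a pair of values. That is a legitimate design, but the plan does not declare it, and Sections 1 and 2 do not pose two questions.

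Finally, there are only two outcomes, both named in advance, so selective emphasis would be visible if both are reported. That limits the harm, but it does not supply an answer when the two disagree.

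The wording of the t-test sentence is not part of the problem. The sentence before it names both pressures, so it is reasonably clear that both changes are tested.

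**Conclusion.** The point holds as an undefined success rule and should be fixed. It does not show that the t-test is invalid, that the sample is too small, or that the error rate is in fact above 5%.

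Its size depends on the rule that is eventually applied. With an either-outcome rule at 5% each, a false claim of benefit has probability about 3.5% to 4.5% against 2.5%, if neither outcome is affected. With a both-outcomes rule and exactly 80% power for each, joint power is about 69% to 75%. Both ranges rest on the assumed correlation of 0.9 down to 0.5 for the error rates and 0.5 up to 0.9 for the power. The absence of a primary outcome, order and rule is certain from the text; the numerical consequences are conditional.

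**What to change.** Before outcomes are compared by arm, add to Section 3:

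- One of the two changes, in mean sleep SBP or in mean sleep DBP, is the primary outcome. The documents do not rank them, so the sponsor chooses.
- The primary is tested at two-sided 5%, and the 80% power statement refers to it.
- The other is tested at two-sided 5% only if the primary is significant; otherwise it is reported as an estimate with a 95% confidence interval.

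**Cost.** Two or three sentences; 66 enrolled and 52 analysed are unchanged. The downside is that the second outcome cannot support a claim alone if the primary is not significant. The documents do not show trial status, so the low cost assumes no comparison by arm has yet been made.

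**Alternatives.**

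- Split alpha at 2.5% each. This is valid if either outcome is meant to suffice. Power per outcome falls from 80% to about 71%, while power for at least one is about 85% to 77% at correlations 0.5 to 0.9. The choice between this and a fixed order is partly one of preference.
- Declare two separate conclusions. This is equally cheap, but the chance of at least one false positive stays at 7.0% to 9.1%, and no single answer on sleep blood pressure is defined.
- Require both. No alpha split is needed, but if each outcome has exactly 80% power at 26 per arm, 80% joint power needs about 30 to 33 per arm at correlations 0.9 to 0.5. That is 60 to 66 analysed and, dividing by 0.80, about 75 to 83 enrolled.

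### The planned t-test on change in sleep blood pressure is valid, but ANCOVA on the same data would usually be more precise and costs at most about one point of power

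*Combined protocol and SAP*

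**What the plan says.** Section 3 defines the outcome as the baseline-to-follow-up change in mean sleep systolic and diastolic pressure, which "will be calculated and compared across randomization arms using a t-test". Means at each visit are also calculated, but only within each arm. No section mentions a baseline covariate, ANCOVA, regression or a mixed model.

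On sample size, Section 3 states: "Sample size calculations used a two-sided alpha of 5% and 80% statistical power". It continues: "Enrolling 66 participants will provide a final sample size of 52", after 10% attrition and 10% incomplete data, and then: "With this sample size, we will have 80% statistical power to detect a change in mean sleep systolic blood pressure and diastolic blood pressure". It gives no effect size, SD or correlation between visits.

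Section 2 fixes the order of measurement. After baseline monitoring, "Participants return the 24-hour devices and are then randomized 1:1", and at the end of the study "participants will repeat the 24-hour blood pressure and heart rate monitoring before returning study devices".

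**The concern.** A t-test on change scores is the same as regressing follow-up pressure on arm with the baseline coefficient set to 1. Randomization makes it unbiased, and it does use the baseline reading. It is the most precise choice, however, only when the true slope of follow-up on baseline is close to 1. Measurement noise and within-person variation between two single 24-hour recordings eight weeks apart would tend to pull the slope below 1. In that case subtracting the whole baseline value adds noise to the comparison.

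The trial is small, enrolment is capped at 66, and the plan claims exactly 80% power at 52 analysed participants, with no stated margin. Precision available from data already collected is therefore worth having. The baseline value is measured before randomization, so it is a legitimate covariate. The change score already needs both readings, so adjustment would lose no additional participants.

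**Working it through.** **Inputs from the documents.** Two-sided alpha 5%, 80% power, 66 enrolled, 52 analysed, 10% attrition and 10% incomplete data (Section 3); 1:1 allocation (Section 2), hence about 26 per arm.

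**Assumptions.** Normal data and the same linear slope in both arms. The correlation r and the follow-up/baseline SD ratio k are not in the documents and are varied below.

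**The plan's own figures.** 66 × 0.80 = 52.8 and 66 × 0.9 × 0.9 = 53.46, so 52 is reproduced to within 2. The 80% power cannot be reproduced without an effect size and SD, so it was inverted. With 26 per arm, 50 degrees of freedom and the noncentral t distribution, power is 80% at a difference of 0.792 SD of change.

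**Variances, with baseline SD = 1.**

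- Change score: 1 + k² − 2rk
- ANCOVA: k²(1 − r²) × (1 + 1/48), with 49 degrees of freedom. The factor 1 + 1/(N − 4), with N = 52, is the average cost of estimating the slope.
- Change minus ANCOVA before that factor: (1 − rk)², which is never negative and is zero only when the true slope rk equals 1. The ratio ANCOVA/change therefore cannot exceed 49/48 = 1.021.

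**Equal SDs (k = 1).** The ratio is (1 + r)/2 × 49/48. At r = 0.7, for example, the change variance is 2(1 − 0.7) = 0.60 and the ANCOVA variance is 0.51 × 49/48 = 0.521, a ratio of 0.868. The noncentrality parameter rises from 0.792 × √13 = 2.86 to 2.86/√0.868 = 3.07, which gives 85.2% power.

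| r | Variance ratio | ANCOVA power (t-test 80%) | Fall in detectable difference |
|---|---|---|---|
| 0.4 | 0.715 | 91.2% | 15% |
| 0.5 | 0.766 | 89.3% | 12% |
| 0.7 | 0.868 | 85.2% | 7% |
| 0.8 | 0.919 | 83.2% | 4% |
| 0.9 | 0.970 | 81.2% | 1.5% |

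The ratio reaches 1 at r = 96/49 − 1 = 0.959.

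**Follow-up SD 20% larger (k = 1.2).**

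| r | Variance ratio | ANCOVA power |
|---|---|---|
| 0.5 | 0.889 | 84.4% |
| 0.7 | 0.986 | 80.5% |
| 0.8 | 1.018 | 79.3% |
| 0.9 | 0.998 | 80.1% |

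**Where ANCOVA does not help.** Setting the ratio to 1 gives k²[(49/48)(1 − r²) − 1] + 2rk − 1 = 0. ANCOVA is no better only between the two roots, and gains on either side.

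| r | SD ratio k | True slope rk |
|---|---|---|
| 0.5 | 1.60–2.67 | 0.80–1.33 |
| 0.7 | 1.25–1.68 | 0.87–1.17 |
| 0.8 | 1.13–1.40 | 0.90–1.12 |
| 0.9 | 1.04–1.19 | 0.93–1.08 |

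**Worst case (true slope exactly 1).** The lost degree of freedom alone takes power from 80.00% to 79.97%. With the slope-estimation factor as well, it is 79.2%, averaged over chance baseline imbalance.

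**Simulation, 40,000 trials per case.** The ANCOVA powers use an average inflation factor inside the noncentral t, so they are approximations. Simulation agrees: with equal SDs, ANCOVA power was 90.9%, 89.5%, 85.3% and 81.5% at r = 0.4, 0.5, 0.7 and 0.9, against 79.6% to 80.5% for the t-test. At slope 1 it was 79.0% and 79.1%. Type I error was 4.8–5.2% for the t-test and 4.9–5.3% for ANCOVA.

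**The case against.** The strongest reply is that nothing is wrong. The t-test is valid, it is prespecified, and it matches a power statement framed in terms of change. On that view, preferring another valid estimator is close to taste. It is true that there is no validity defect, and none is claimed here. The preference still rests on a lopsided trade: a loss of at most about 0.8 power points on average, against a gain of 1 to 11 points with equal SDs and r between 0.4 and 0.9.

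The second reply is that the gain cannot be sized from the documents, and this stands. Every power figure above depends on an assumed r and SD ratio, and takes the plan's 80% as given. At high r the gain is also fragile. If follow-up SD is only 10% larger than baseline SD, ANCOVA power is 82.3%, 80.4% and 79.2% at r = 0.7, 0.8 and 0.9. The uncertainty runs both ways, though: with follow-up SD 10% smaller and r = 0.7, it is 89.2%.

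The third reply concerns timing. The document is dated July 11, 2025 and does not give the trial's status. If outcome data by arm have been seen, replacing the main analysis would be a post hoc choice. This also stands, and the recommendation is conditional on it.

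**Conclusion.** The concern holds, as an efficiency improvement and not as an error. The only stated between-arm analysis fixes the baseline slope at 1, although a pre-randomization baseline is available to estimate it. With 26 per arm and equal SDs, ANCOVA raises power from 80% to between 81% (r = 0.9) and 91% (r = 0.4). Where the true slope is near 1 the gain is nil or slightly negative, down to 79.2%. The direction of the trade is secure, because the variance ratio cannot exceed 1.021 under the assumptions used. The size of the gain is not secure, because the documents give neither the correlation nor the SDs.

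**What to change.** Before outcome data by arm are seen, replace the t-test sentence in Section 3 with:

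> Follow-up mean sleep SBP and, separately, DBP will be compared between arms by ANCOVA with randomized arm and the corresponding baseline mean sleep BP as covariate, reporting the adjusted difference and 95% CI; the t-test on change from baseline will be reported as a supportive analysis.

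The cost is one sentence. It needs no new data and no extra participants, since both analyses use the same two readings. The statistical price is one degree of freedom and about 2% in variance for estimating the slope. If outcome data by arm have already been seen, the t-test should stay as the main analysis and ANCOVA should be reported only as supplementary. Stating the assumed correlation and SDs would let the authors size the gain, but the switch does not depend on it.

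### Baseline sleep blood pressure is recorded before assignment, but no stratification on it is stated and the primary t-test on change does not adjust for it

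*Combined protocol and SAP*

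**What the plan says.** The title names nocturnal hypertension. The Background defines it as sleep blood pressure of at least 110/65 mmHg, pairs it with non-dipping, and says of the two: "These patterns are present in 30–45% of the general population, but optimal strategies to address them remain unclear". The purpose in Section 1 is broader: "The purpose of this study is to examine the impact that sleep duration has on blood pressure levels during sleep".

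In Section 4 (Recruitment) the criterion that selects participants is "Sleep duration < 7 hours per night as assessed via daily self-report of sleep hours". No inclusion or exclusion item refers to blood pressure level, and the 110/65 threshold does not appear again after the Background.

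On allocation, Section 2 (Study Design) says: "Participants return the 24-hour devices and are then randomized 1:1 to either a sleep hygiene/extension education program or control education". The baseline 24-hour recording therefore exists before assignment. No stratification or minimization factor is named.

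Section 3 (Statistical Procedures) compares the arms on change in mean sleep systolic and diastolic pressure by a t-test, with no covariate. No subgroup or interaction analysis is described.

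**The concern.** The condition in the title and rationale plays no stated part in entry, allocation or analysis. Section 3 expects about 26 analysed participants per arm, so the number with elevated sleep blood pressure can differ noticeably between arms by chance. An arm that starts higher by chance tends to fall further through regression to the mean. A t-test on change scores does not remove that, because subtracting baseline is not the same as adjusting for it.

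At stake are the precision of the primary comparison and the reading of a single small trial. If the arms differ visibly at baseline, readers will ask how much of the result reflects that difference, and the plan has no prepared answer. Nor does it say how far the overall result speaks to nocturnal hypertension.

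**Working it through.** **Inputs from the plan.** 66 enrolled, 52 analysed, 10% attrition, 10% incomplete data, two-sided alpha 5%, power 80% (Section 3); 1:1 allocation after the devices are returned (Section 2); 30–45% in the general population (Background). Not given: effect size, SD, baseline/follow-up correlation, and prevalence among short sleepers.

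**1. The plan's own figure.** 66 × (1 − 0.20) = 52.8, or 66 × 0.9 × 0.9 = 53.46. The stated 52 is reproduced within two participants, giving 26 per arm. The 80% power cannot be reproduced without an effect and SD. With 26 per arm, a two-sided 5% t-test has 80% power for a difference of 0.79 SD of the change score.

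**2. Number affected, if 30–45% applied.** 66 × 0.30 = 19.8 and 66 × 0.45 = 29.7, so about 20 to 30. Among 52 analysed: 15.6 to 23.4.

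**3. Chance imbalance without stratification.** With K affected among 66 and 33 per arm, the number X in one arm is hypergeometric and the gap is |2X − K|. The SD of 2X − K is 2 × √[33 × (K/66) × (1 − K/66) × 33/65].

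| K affected | SD of gap | P(gap ≥ 6) | P(gap ≥ 8) |
|---|---|---|---|
| 20 | 3.8 | 0.18 | 0.06 |
| 30 | 4.1 | 0.22 | 0.08 |

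A gap of 6 is 6/33 = 18 percentage points; a gap of 8 is 24 points. The gap has the same parity as K, so for odd K between 21 and 29 a gap of 6 or more means at least 7, with probability 0.11 to 0.14. If K itself varies binomially, P(gap ≥ 6) averages 0.14 at 30% and 0.17 at 45%. One in five is thus the upper end of a range starting near one in seven. Higher prevalence does not remove the issue: at 60% the average is 0.17.

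Among 52 analysed, the SD of the difference in proportions is √[2p(1 − p)/26] = 0.127 (p = 0.30) to 0.138 (p = 0.45).

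**4. What the change-score t-test leaves behind.** Assume equal variances at both visits and correlation ρ. A chance baseline difference D contributes (ρ − 1) × D to the expected difference in change. At ρ = 0.6 that is −0.4D. Adjusting for baseline removes it and multiplies the variance by (1 − ρ²)/[2(1 − ρ)] = (1 + ρ)/2.

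| Assumed ρ | Variance ratio | Power, t-test on change | Power, baseline-adjusted |
|---|---|---|---|
| 0.4 | 0.70 | about 80% | about 91% |
| 0.6 | 0.80 | about 79% | about 87% |
| 0.8 | 0.90 | about 80% | about 83% |

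Powers are from simulation (bivariate normal, 52 analysed, 20,000 trials per setting, true effect 0.79 SD of the change score).

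**5. Stratifying without adjusting.** In the same simulation, with two strata cut at the top 30% or 45% of baseline, keeping the unadjusted t-test gave type I error of about 3% (ρ = 0.4) to 4% (ρ = 0.8) instead of 5%, because its standard error ignores the balance achieved. With baseline in the model it returned to 5%. Once baseline was adjusted for, stratification changed power by about one percentage point or less. The adjustment supplies nearly all the statistical gain; stratification mainly supplies visible balance.

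**6. Precision in the elevated group.** 52 × 0.30/2 = 7.8 and 52 × 0.45/2 = 11.7 per arm. A difference detectable with 80% power is then about 1.5 or 1.2 SD.

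**The case against.** The strongest reply is that the target population is stated and is short sleepers. The purpose concerns the level of sleep blood pressure, the outcome is continuous, and the entry criterion selects people with the exposure to be changed. That stands: the missing blood pressure criterion is not a contradiction and entry should stay open.

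Three stronger readings are tempting, and the documents support none of them.

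- *Most participants lack the condition.* The 30–45% is for the general population and for two patterns named together, not for 110/65 mmHg alone. The Background also says: "Prior studies show that insufficient sleep is linked to higher nighttime blood pressure and non-dipping patterns". The share would pass one half if short sleepers had odds 0.55/0.45 = 1.22 times (from 45%) to 0.70/0.30 = 2.33 times (from 30%) those of the general population. The sleep apnoea exclusion may push the other way, so the direction is unknown.
- *The overall effect is diluted by a known amount.* Any such figure needs an effect size and an assumed zero effect below the threshold. The plan gives neither.
- *The comparison is biased.* Chance imbalance under randomization causes no average bias and does not raise type I error. The baseline recording also does enter the analysis, through the change score.

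Finally, a short document that names no stratification factor does not prove that none is used. If one is used, stating it and matching the analysis to it meets much of this point.

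**Conclusion.** The point holds as a matter of efficiency and interpretation, not validity. A strong prognostic measurement is in hand before assignment, and the plan states no use of it beyond subtraction. A gap of six or more affected participants is plausible: 0.18 to 0.22 with exactly 20 or 30 affected, 0.14 to 0.17 averaged over the number affected. Those figures assume that 30–45% carries over to this sample, that the arms are equal in size, and that allocation is unstratified. The gain from adjustment, about 79% to 87% power, assumes a correlation of 0.6 and equal variances; it is larger at lower correlations and smaller at higher ones. The improvement is inexpensive and worth making.

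**What to change.** 1. Leave entry open.
2. If enrolment allows, stratify the 1:1 randomization, with blocks within strata, by baseline mean sleep blood pressure category at the plan's own 110/65 mmHg. State whether both components or either one must reach the threshold, and how a participant with an unusable baseline recording is assigned. If enrolment is too advanced, omit this step.
3. In either case, replace the t-test in Section 3 with a linear model for follow-up mean sleep blood pressure, one for systolic and one for diastolic. Include arm, the continuous baseline value of the same measure, and the stratum if used.
4. Report the treatment-by-baseline-sleep-blood-pressure interaction with its 95% CI, labelled exploratory.
5. State that the overall result applies to short sleepers regardless of blood pressure.

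Cost: the monitor must be read before assignment if step 2 is adopted, and one extra table is needed. No additional recruitment or measurement is required. Any estimate in the elevated group, with about 8 to 12 per arm if 30–45% applies, will be imprecise and should be presented that way.
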